*** Outcomes analyses:**

The two groups will be compared at baseline on demographic features, life style characteristics, knowledge and attitudes to antihypertensive drug therapy, as well as medical use, by *t*-test for continuous variables and chi-square test for binary variables. Regression model for longitudinal data will be applied to examine the effects of intervention on the changes of primary and secondary variables from baseline during follow-up. The software of SPSS 16.0 (SPSS, Inc., Chicago, IL) will be used for baseline comparisons and mixed effects linear model, and Stata 10 for mixed effects logistic model.

References:

1. Ministry of Health. Health Statistics Yearbook 2010. Beijing: Ministry of Health; 2011.

Title of project: Effects of individualized antihypertensive information on the medication use in hypertensive patients: An exploratory randomized controlled trial.
Principle investigator: [name]

-
2. Medscape Website. Global diversity in hypertension: lessons learned. Accessed at <http://www.medscape.com/viewarticle/746194> on May 19, 2013.
 4. NICE Website. Lipid modification: Cardiovascular risk assessment and the modification of blood lipids for the primary and secondary prevention of cardiovascular disease. Accessed at <http://www.nice.org.uk/CG67> on May 10, 2013.
 9. Informed medical decisions foundation Website. What is shared decision making? Accessed at <http://informedmedicaldecisions.org/what-is-shared-decision-making/> on May 12, 2013.

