Since the CVD events estimated by Fuwai equation are mainly the ischemic ones, the estimated probabilities are adjusted based on the ratio of incidences of coronary heart diseases and cerebrovascular diseases (21), as well as that of incidences of ischemic and hemorrhagic cerebrovascular diseases (22) in the Chinese population.

(2) Estimated absolute risk reduction by antihypertensive drug therapy, calculated as follow:

$$\text{Absolute risk reduction (ARR)} = \text{Baseline risk} \times \text{Relative risk reduction (RRR)}$$

RRR: from a systematic review published within 5 years before this study (3);

(3) Medicinal side effects and the estimated probabilities;

(4) Estimated monetary costs of antihypertensive medicines each year;

(5) Qualitative description of opportunistic costs of not initiating pharmaceutical therapy.

4. Outcomes of interest:

* Primary outcomes:

(1) Rate of treatment:

$$\text{Treatment rate} = \frac{\text{Patients currently on antihypertensive medication}}{\text{Total number of patients}} \times 100\%$$

Patients currently on antihypertensive medication are defined as those who took antihypertensive medicines in the past two weeks.

(2) Rate of good adherence:

$$\text{Rate of good adherence} = \frac{\text{Patients with good adherence}}{\text{Total number of patients}} \times 100\%$$

Patients with good adherence are defined as those with percentage of tablets taken as prescribed over 80% in the past week.

* Secondary outcomes:

(1) Changes of willingness to take antihypertensive medicines, obtained at the end of the intervention;

(2) Life style information by self-report, in the past two weeks before the time points of follow-up:

- a. Amount of cigarette smoked per week;
- b. Amount of alcohol consumed per week;
- c. Amount of physical exercises per week in considering of duration and intensity;
- d. Change of amount of salt intake;
- e. Change of amount of fat intake.

5. Implementation of the study:

Title of project: Effects of individualized antihypertensive information on the medication use in hypertensive patients: An exploratory randomized controlled trial.
Principle investigator: [name]

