*** Follow-up:**

Title of project: Effects of individualized antihypertensive information on the medication use in hypertensive patients: An exploratory randomized controlled trial.
 Principle investigator: [name]

Interviewers will be in charge of patients' follow-up. Telephone interview will be conducted at two weeks, three months, and six months after the intervention. Patients in the control group will receive the individualized antihypertensive information in the last time follow-up. Contents of the survey include:

- (1) Medication use of antihypertensive treatments;
- (2) Life style changes;
- (3) Knowledge and attitudes to antihypertensive treatments;
- (4) Any possible contamination during the study, doctors' attitudes and the effects on patients decisions or behaviors.

6. Statistical analyses:

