*** Sample size calculation:**

$$n = \frac{2(u_\alpha + u_\beta)^2 \bar{P}(1 - \bar{P})}{(P_1 - P_2)^2}$$

Inequality test for two proportions is applied in the calculation.

Sample sizes in two groups are assumed to be equal.

$\alpha = 0.05$ (For preplanned subgroup analysis: on/ not on antihypertensive drug therapy);

Power: $1 - \beta = 0.80$

Rate difference between groups: $\Delta P = 0.20$

Pharmacological treatment rate in control: $P_1 = 0.75$

$n_1 = n_2 = 90$

A total of 100 patients are going to be recruited in each group, when the rate of loss to follow up is assumed to be 10%.

This predefined sample size in each group is able to detect the difference of 0.20 in rate of good adherence between groups, with the significant level of 0.05, power of 0.80 and the baseline rate of 0.40.

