Baseline	71 (66.4)	72 (69.9)	1.22 (0.68, 2.18)	.512
Third follow-up	76 (71.0)	71 (68.9)	0.91 (0.50, 1.63)	.740
Cutoff value=5				
Baseline	71 (66.4)	72 (69.9)	1.18 (0.66, 2.11)	.581
Third follow-up	75 (70.1)	70 (68.0)	0.91 (0.50, 1.63)	.739
Cutoff value=6				
Baseline	71 (66.4)	71 (68.9)	1.13 (0.63, 2.01)	.691
Third follow-up	74 (69.2)	70 (68.0)	0.95 (0.53, 1.69)	.852
Cutoff value=7				
Baseline	69 (64.5)	71 (68.9)	1.22 (0.69, 2.17)	.496
Third follow-up	73 (68.2)	69 (67.0)	0.95 (0.53, 1.69)	.849
Cutoff value=8				
Baseline	65 (60.7)	70 (68.0)	1.37 (0.78, 2.42)	.277
Third follow-up	63 (58.9)	67 (65.0)	1.30 (0.74, 2.27)	.357
Cutoff value=9				
Baseline	65 (60.7)	68 (66.0)	1.26 (0.72, 2.20)	.429
Third follow-up	63 (58.9)	67 (65.0)	1.30 (0.74, 2.27)	.357
Cutoff value=11				
Baseline	61 (57.0)	64 (62.1)	1.30 (0.75, 2.28)	.349
Third follow-up	61 (57.0)	67 (65.0)	1.40 (0.80, 2.45)	.233
Cutoff value=12				
Baseline	59 (55.1)	63 (61.2)	1.28 (0.74, 2.22)	.420
Third follow-up	59 (55.1)	67 (65.0)	1.51 (0.87, 2.64)	.143
Cutoff value=13				
Baseline	57 (53.3)	60 (58.3)	1.20 (0.69, 2.07)	.514

Third follow-up	58 (54.2)	61 (59.2)	1.23 (0.71, 2.12)	.463
Cutoff value=14				
Baseline	55 (51.4)	55 (53.4)	1.08 (0.63, 1.86)	.827
Third follow-up	57 (53.3)	57 (55.3)	1.09 (0.63, 1.87)	.764

Abbreviations: OR, odds ratio; CI, confidence interval.

S4 Table. Sensitivity analyses: effects of individualized, evidence-based counseling on good adherence to treatment when different cutoff values were employed to define the outcome

Outcome variable	Control	Intervention	OR (95% CI)	P value
Cutoff value=10%				
Baseline	75 (70.1)	74 (71.8)	1.09 (0.60, 1.98)	.780
Third follow-up	78 (72.9)	72 (69.9)	0.86 (0.47, 1.57)	.631
Cutoff value=20%				
Baseline	73 (68.2)	73 (70.9)	1.13 (0.63, 2.04)	.677
Third follow-up	76 (71.0)	71 (68.9)	0.91 (0.50, 1.63)	.741
Cutoff value=30%				
Baseline	71 (66.4)	72 (69.9)	1.18 (0.66, 2.11)	.581
Third follow-up	75 (70.1)	70 (68.0)	0.91 (0.50, 1.63)	.739
Cutoff value=40%				
Baseline	71 (66.4)	71 (68.9)	1.13 (0.63, 2.01)	.691
Third follow-up	74 (69.2)	70 (68.0)	0.95 (0.53, 1.69)	.852
Cutoff value=50%				
Baseline	69 (64.5)	71 (68.9)	1.22 (0.69, 2.17)	.496
Third follow-up	73 (68.2)	69 (67.0)	0.95 (0.53, 1.69)	.849
Cutoff value=60%				
Baseline	65 (60.7)	68 (66.0)	1.26 (0.72, 2.20)	.429
Third follow-up	63 (58.9)	67 (65.0)	1.30 (0.74, 2.27)	.357
Cutoff value=70%				
Baseline	61 (57.0)	64 (63.4)	1.30 (0.75, 2.28)	.351

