Third follow-up	61 (57.0)	67 (65.0)	1.40 (0.80, 2.45)	.234
Cutoff value=80%				
Baseline	59 (55.1)	63 (61.2)	1.28 (0.74, 2.22)	.420
Third follow-up	59 (55.1)	67 (65.0)	1.51 (0.87, 2.64)	.143
Cutoff value=90%				
Baseline	57 (53.3)	60 (58.3)	1.20 (0.69, 2.07)	.514
Third follow-up	58 (54.2)	61 (59.2)	1.23 (0.71, 2.12)	.463
Cutoff value=100%				
Baseline	55 (51.4)	55 (53.4)	1.08 (0.63, 1.86)	.827
Third follow-up	57 (53.3)	57 (55.3)	1.09 (0.63, 1.87)	.764

Abbreviations: OR, odds ratio; CI, confidence interval.

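### The visible odds ratios in S3 and S4 are unadjusted cross-sectional comparisons, so they do not test whether the planned longitudinal estimate is robust to the cut-off

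*Combined protocol and SAP*

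**What the plan says.** The Outcomes analyses section sets the model for primary and secondary outcomes: "Regression model for longitudinal data will be applied to examine the effects of intervention on the changes of primary and secondary variables from baseline". For software it names "Stata 10 for mixed effects logistic model", which is the natural choice for the two binary primary outcomes.

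Repeated measurements are planned. Medication use is recorded in the baseline survey, and under Follow-up, "Telephone interview will be conducted at two weeks, three months, and six months after the intervention". The third follow-up is therefore the six-month interview.

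Under Outcomes of interest, "Patients with good adherence are defined as those with percentage of tablets taken as prescribed over 80% in the past week". S4 varies that threshold from 10% to 100% and is headed "Sensitivity analyses: effects of individualized, evidence-based counseling on good adherence to treatment when different cutoff values were employed". S3 does the same for drug use, with cut-offs in days. For each cut-off both tables print one OR at baseline and a separate one at the third follow-up. The visible parts show no change, arm-by-time or baseline-adjusted estimate, and the footnotes only expand the abbreviations. The protocol text itself specifies no sensitivity analysis and no model for one.

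**The concern.** A sensitivity analysis of an outcome definition should vary the definition and hold the estimator fixed. The plan's estimator concerns change from baseline and uses the repeated measurements. The tables instead appear to compare the arms at six months alone, without reference to where each arm started.

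This matters because the arms did not start level on the outcome itself. The printed baseline ORs run from 1.08 to 1.37, all above 1. A reader who takes the follow-up column as the effect of counselling gets figures that ignore this imbalance, and cannot learn from them whether the planned result survives a change of cut-off.

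**Working it through.** **Inputs.** Counts and percentages from S3 and S4. The denominators follow from the 80% row of S4: 59/0.551 gives 107 (control) and 67/0.650 gives 103 (intervention).

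**Step 1: reproduce the printed figure.** With *a* intervention and *c* control patients meeting the definition:

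OR = [a/(103 − a)] / [c/(107 − c)]; SE(ln OR) = √[1/a + 1/(103 − a) + 1/c + 1/(107 − c)].

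S4, 80%, third follow-up: (67/36)/(59/48) = 1.51. SE = √(1/67 + 1/36 + 1/59 + 1/48) = 0.284. The 95% CI is exp(ln 1.514 ± 1.96 × 0.284) = 0.87 to 2.64, and the uncorrected chi-square P is .143. All match the print.

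The same formula reproduces all 20 visible third-follow-up ORs and CIs (ten rows in each table) to two decimals, with P values within about .001. A mixed or baseline-adjusted model would not be expected to match the crude tables in every row.

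**Step 2: the baseline position.** S4, 80%: (63/40)/(59/48) = 1.28 (0.74, 2.22), as printed. From the counts, the follow-up difference is 67/103 − 59/107 = 9.9 points and the baseline difference is 63/103 − 59/107 = 6.0 points. The difference in change is 3.9 points.

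**Step 3: a descriptive contrast across S4.** The ratio is the follow-up OR divided by the baseline OR, both from the counts (control/intervention).

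| Cut-off | Baseline | Follow-up | Follow-up OR | Ratio |
|---|---|---|---|---|
| 10% | 75/74 | 78/72 | 0.86 | 0.79 |
| 20% | 73/73 | 76/71 | 0.91 | 0.80 |
| 30% | 71/72 | 75/70 | 0.91 | 0.77 |
| 40% | 71/71 | 74/70 | 0.95 | 0.84 |
| 50% | 69/71 | 73/69 | 0.95 | 0.77 |
| 60% | 65/68 | 63/67 | 1.30 | 1.04 |
| 70% | 61/64 | 61/67 | 1.40 | 1.13 |
| 80% | 59/63 | 59/67 | 1.51 | 1.18 |
| 90% | 57/60 | 58/61 | 1.23 | 1.00 |
| 100% | 55/55 | 57/57 | 1.09 | 1.00 |

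The CI of a ratio depends on the correlation between the two log ORs, which the documents do not give. For the 80% row it is 0.54–2.58 at an assumed correlation of 0, 0.68–2.05 at 0.5 and 0.83–1.68 at 0.8.

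Some printed baseline entries do not fit 107 and 103. At 70%, S4 prints 63.4% and an OR of 1.30, but 64/103 is 62.1% and gives 1.24. At 90% the printed OR is 1.20 and the counts give 1.22. With the printed ORs the ratios would be 1.40/1.30 = 1.08 and 1.23/1.20 = 1.03. The second decimal of a ratio should not be leaned on.

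**Step 4: what baseline adjustment might give.** For the 80% row I fixed each arm's baseline and follow-up totals and assumed a within-arm correlation (phi) between the two binary measurements. I then fitted follow-up status on arm and baseline status, with a logistic model for the OR and a linear model for the risk difference.

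| Assumed phi | Adjusted OR | Adjusted risk difference (points) |
|---|---|---|
| 0 | 1.51 | 9.9 |
| 0.2 | 1.46 | 8.7 |
| 0.4 | 1.45 | 7.5 |
| 0.6 | 1.51 | 6.3 |
| 0.8 | 1.82 | 5.1 |

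The adjusted OR stays near the crude 1.51 or rises above it. The adjusted risk difference shrinks, but not to 3.9 points over this range.

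**The case against.** The strongest reply is that the trial is randomised. An unadjusted six-month comparison is unbiased over randomisations, and the imbalance is the non-significant kind that chance produces. The baseline OR is printed directly above each follow-up OR, so nothing is concealed. No follow-up result is significant (smallest P .143). The plan does not say which model a sensitivity analysis must use.

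All of that stands, and it limits the point. It does not answer it. Given the imbalance actually observed, the crude OR is not the planned change-from-baseline quantity, and the tables give no estimate with a CI that accounts for the baseline.

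Three stronger readings are tempting and not supported.

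- *The true effect at 80% is 1.18, or 3.9 points, and the rest is bias.* That comes from subtracting the baseline difference in full. Step 4 shows that baseline adjustment need not do so. The planned mixed logistic OR is subject-specific, so a ratio of marginal ORs does not estimate it either.
- *The tables hide a harmful effect at cut-offs of 50% or less.* The printed ORs there are already below 1 (0.86–0.95). The ratios of 0.77–0.84 are imprecise: at 50% the CI is 0.34–1.75 at an assumed correlation of 0 and 0.54–1.11 at 0.8.
- *The estimator was switched between the main and the sensitivity analysis.* The documents examined contain no primary result, so this cannot be judged.

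**Conclusion.** The concern holds as a mismatch between plan and tables. The plan calls for a longitudinal model of change from baseline; the visible follow-up ORs in S3 and S4 are crude six-month comparisons presented as effects. They leave a chance baseline imbalance in the same outcome unaccounted for, and they cannot show whether the planned estimate is robust to the cut-off.

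The size of the consequence is not known. The ratio of follow-up to baseline ORs (1.18 at 80%, 0.77–1.18 across S4) indicates that the picture may change, no more. The planned estimate cannot be computed without patient-level data, and a baseline-adjusted OR could be close to the printed 1.51 or above it. No false-positive finding is created.

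The crude match rests on denominators of 107 and 103, inferred from the printed percentages. It covers only the visible rows: the text examined begins partway through S3, so its lower cut-offs and any model note there were not checked. A note could not alter the match in the rows that were.

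**What to change.** Re-run every row of S3 and S4 with the planned mixed effects logistic model and report the arm-by-time effect at six months. If that model is not feasible, use a six-month logistic model adjusted for the same outcome at baseline. Use one model for all rows, name it in a footnote, and present its estimate with the 95% CI as the effect.

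Keep the existing ORs if wanted, labelled as unadjusted. The baseline rows may stay as description, in line with the plan's own baseline comparison of the groups. Check the baseline entries that do not agree with their counts while the tables are open.

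The cost is a few hours of programming on existing data, and possibly wider confidence intervals.

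### The effect is worded as change from baseline with no baseline adjustment stated; on the ordinary reading this wastes precision and does not match the test used for sizing

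*Combined protocol and SAP*

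**What the plan says.** Section 6, Outcomes analyses, plans a longitudinal regression whose purpose is to "examine the effects of intervention on the changes of primary and secondary variables from baseline during follow-up". Binary outcomes go to "Stata 10 for mixed effects logistic model"; a mixed linear model is named as well. The paragraph does not say whether baseline enters as a covariate, whether the arms share one baseline mean, or which model term or visit is the primary test. It also plans significance tests between the arms at baseline.

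Section 6, Sample size calculation, states: "Inequality test for two proportions is applied in the calculation". Its formula contains no baseline or correlation term.

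Section 5 places the baseline survey, including medication use and lifestyle, ahead of randomisation. It then schedules telephone follow-up at two weeks, three months and six months. Section 4 defines the salt and fat outcomes as self-reported changes in amount.

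**The concern.** In a randomised trial the expected arm difference at baseline is zero. A change contrast with a free baseline arm difference estimates that known zero from the data and subtracts it, which adds noise. It also removes the whole of a chance baseline imbalance, when only the part that persists to follow-up should go. Adjusting for baseline avoids both problems with data the trial already holds. This does not depend on the random-effects structure or the standard errors; it applies to a correctly specified model.

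At stake is precision on both primary outcomes and on the secondary outcomes that have a baseline level. In addition, the stated power belongs to an analysis other than the one described.

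**Working it through.** **Inputs from the documents.** Sample size calculation: alpha 0.05, power 0.80, difference 0.20, control treatment rate 0.75, 90 evaluable per arm (100 recruited, 10% loss); for adherence, baseline rate 0.40 and difference 0.20. Follow-up: three interviews.

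**Assumptions.** Two-sided alpha (sidedness is not stated, but two-sided reproduces 90). Correlation ρ of 0.3, 0.5 and 0.7, equal between all pairs of visits, with equal variance σ² at each visit.

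**1. The plan's own figure.** n = 2(1.96 + 0.842)² P̄(1 − P̄)/(P₁ − P₂)².
- Treatment, 0.75 v 0.55: 2 × 7.849 × 0.2275/0.04 = 89.3, so 90; 90/0.9 = 100. The plan is reproduced.
- Treatment, 0.75 v 0.95 (the direction in the Hypothesis section): 2 × 7.849 × 0.1275/0.04 = 50.0. This does not give 90.
- Adherence, 0.40 v 0.60: 2 × 7.849 × 0.25/0.04 = 98.1, so 99.

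**2. Variance per patient, in units of σ².**
- One visit: change 2(1 − ρ); follow-up alone 1; baseline-adjusted 1 − ρ².
- Mean of three visits: change (4 − 4ρ)/3; follow-up alone (1 + 2ρ)/3; adjusted (1 + 2ρ)/3 − ρ².

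| Change v adjusted | ρ = 0.3 | ρ = 0.5 | ρ = 0.7 |
|---|---|---|---|
| One visit | 1.40/0.91 = 1.54 | 1.00/0.75 = 1.33 | 0.60/0.51 = 1.18 |
| Three visits | 0.933/0.443 = 2.11 | 0.667/0.417 = 1.60 | 0.400/0.310 = 1.29 |

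For one visit, adjusted/change = (1 + ρ)/2, which is below 1 for every ρ below 1. Change equals follow-up alone where 2(1 − ρ) = 1, or (4 − 4ρ) = (1 + 2ρ). Both give ρ = 0.5; below that, change is worse than ignoring baseline. Averaging visits widens the gap to adjustment, because the single baseline is not averaged.

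**3. Power at 90 per arm.** Power = Φ(2.802 √(90/(n₈₀ f)) − 1.96), with f the variance factor above and n₈₀ = 89.3 or 98.1. Example: treatment, one visit, change, ρ = 0.3: 2.802 × √(90/(89.3 × 1.4)) − 1.96 = 0.42, giving 66%.

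| Change / adjusted | ρ = 0.3 | ρ = 0.5 | ρ = 0.7 |
|---|---|---|---|
| Treatment 0.75 v 0.55, one visit | 66% / 84% | 80% / 90% | 95% / 98% |
| Treatment 0.75 v 0.55, three visits | 83% / 99% | 93% / 99% | 99% / >99% |
| Adherence 0.40 v 0.60, one visit | 62% / 80% | 77% / 87% | 93% / 96% |
| Adherence 0.40 v 0.60, three visits | 79% / 98% | 91% / 99% | 99% / >99% |

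A plain follow-up comparison (f = 1) has 80% for treatment and about 77% for adherence.

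**4. Correlation at which change reaches 80%**, from f = 90/n₈₀:
- Treatment 0.75 v 0.55: f = 1.008, so ρ = 0.50 with one visit and 0.24 with three.
- Adherence: f = 0.917, so ρ = 0.54 and 0.31.
- Treatment 0.75 v 0.95: f = 1.80, so ρ = 0.10 with one visit (0.27 with variances specific to each proportion); with three visits, no shortfall at any ρ of 0 or more.

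**5. Check on the logistic scale.** The formulas are for a linear scale. Simulated logistic models, one visit, 90 per arm, arm-by-time v baseline-adjusted:
- 0.75 v 0.55: 64% v 84% at correlation about 0.31; 73% v 89% at 0.47.
- 0.40 v 0.60: 61% v 81% at about 0.33; 75% v 87% at 0.49.
- 0.75 v 0.95: 87% v 96% at 0. The two meet near 0.47 (both 98%), and change is slightly ahead at 0.63 (99.0% v 98.4%) and 0.78 (100% v 97.4%), all far above 80%.

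A random-intercept logistic simulation of the adherence case with one follow-up (300 runs per setting) gave 60%, 71% and 86% with a free baseline arm effect. With a common baseline it gave 80%, 87% and 91%. The correlations were 0.24, 0.42 and 0.59.

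**The case against.** **The model criticised is partly inferred.** The plan does not say that the baseline arm difference is left free. A mixed model with baseline as a response and one common baseline mean also describes change from baseline, and is about as efficient as adjustment. This stands as a limit. The free term is the likelier reading, since the same paragraph tests the arms against each other at baseline, but it is not written down. If a common baseline was intended, the plan still needs to say so.

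**A reader might infer that the trial misses 80% power whenever the correlation is below about 0.5.** The documents do not support that as a general statement. It holds for one visit with 0.75 v 0.55. The plan has three follow-ups and names no primary visit; averaging them lowers the threshold to about 0.24 to 0.31, and the hypothesised increase to 0.95 lowers it further. No correlation is given, and at 0.6 or more change exceeds 80% in every case computed.

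**The adherence shortfall is not caused by the change analysis.** At 90 per arm a plain follow-up comparison has only about 77%. That comes from the sizing arithmetic.

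**The S4 table does not settle the matter.** In its 80% row the arms differ by 63/103 − 59/107 = 6.0 points at baseline and 67/103 − 59/107 = 9.9 points at third follow-up, so simple change is 3.9 points. The reported odds ratio of 1.51 is the crude follow-up ratio, (67 × 48)/(36 × 59). It uses neither change nor adjustment, and it is a result that does not define the planned model.

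**Not every secondary outcome is affected.** Salt and fat intake are defined as reported changes, so they have no baseline value of the same variable.

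**Conclusion.** The concern holds as a loss of precision and a mismatch within the plan. The effect is worded as change from baseline, with no adjustment or common baseline mean stated. Fitted with a free baseline arm difference, it has 54%, 33% or 18% more variance than the adjusted analysis for one visit at ρ = 0.3, 0.5 or 0.7, and 111%, 60% or 29% more for the mean of three visits. The ordering at every ρ below 1 is a linear-scale result. The logistic simulations agree for the two cases 0.75 v 0.55 and 0.40 v 0.60, but not at high correlation for 0.75 v 0.95, where power is ample either way.

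These sizes rest on assumed, equal correlations and on the ordinary reading of the model. A power failure is not established. It would also be wrong to claim the stated 80% for an adjusted analysis: at 0.75 v 0.55 and one visit, adjustment needs about 82 per arm at ρ = 0.3 and 67 at ρ = 0.5, so the formula behind 90 is not that of an adjusted test. For an exploratory trial this is a worthwhile correction to the analysis section; it does not invalidate the design.

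**What to change.** In Outcomes analyses, define the effect, for every outcome with a baseline level, as the arm difference at follow-up adjusted for the baseline value of the same variable. Either form will do:
- baseline as a covariate in the mixed logistic or mixed linear model of the follow-up visits; or
- baseline kept as a response, with visit terms, one common baseline mean for both arms, and arm-by-follow-up-visit terms (no arm main effect).

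Name the primary visit, or state that the visits are averaged. Compare salt and fat intake directly between arms, as self-reported change.

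In Sample size calculation, label the figures as those of an unadjusted follow-up comparison of two proportions. Do not state that they were calculated for the adjusted analysis.

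The cost is a few sentences and one model term. No new data or patients are needed.
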